2.7. Transparency in Research

Prior to the recruitment of the first participant, the trial will have been registered on a publicly accessible trial registry. Results will be uploaded to the registry within 12 months of the end of trial declaration by the responsible party. Where the trial has been registered on the public platform, the trial information will be kept up to date during the trial, and the responsible party will upload results to the public registry within 12 months of the end of the trial declaration.

2.8. Quality Control and Quality Assurance

The study will be conducted in accordance with the current approved protocol, ICH GCP, relevant regulations and standard operating procedures. Data will be evaluated for compliance with the protocol and accuracy in relation to source documents. Following written standard operating procedures, the independent monitors from Clinical Trials Support Group (CTSG), MORU will verify that the clinical trial is conducted and data are generated, documented and reported in compliance with the protocol.

2.9. Publication and Data Policy

All Investigators will be involved in reviewing drafts of the manuscripts, abstracts, press releases and any other publications arising from the study. Authorship will be determined in accordance with the International Committee of Medical Journal Editors (ICMJE) guidelines and other contributors will be acknowledged.

2.10. Sponsor and Insurance

Sponsor name: University of Oxford

Contact information: [name]

The study sponsor has a role in the design of the study; collection of data; management, analysis, and interpretation of data; writing of the report; and the decision to submit the report for publication.

The University of Oxford has a specialist insurance policy in place: - Newline Underwriting Management Ltd, at Lloyd's of London – which would operate in the event of any participant suffering harm as a result of their involvement in the research.

2.11. Financing

The funder, Medical Research Council, had a role in the design of the study. The funder will not have any role in its execution, analyses, and interpretation of data or decision to submit results.

**Research Proposal Submission Form
for a study involving human subject enrollment WITH
specimen collection**

Document No.: FTM ECF-033-01

Page 49 of 52

APPENDIX C: LIST OF ABBREVIATIONS

ACT	Artemisinin combination therapy
AE	Adverse event
ALT	Alanine aminotransferase
anti-CS	Antibody to the P. falciparum circumsporozoite (CS) repeat domain
anti-HBs	Antibody to the hepatitis B surface antigen
Anti-HCV	Antibody to hepatitis C virus
AST	Aspartate aminotransferase
CI	Confidence interval
CREA	Creatinine
CRF	Case report form
CSP	Circumsporozoite protein of P. falciparum
CTU	Clinical Therapeutics Unit (CTU), Hospital for Tropical Diseases, Faculty of Tropical Medicine, Mahidol University
DHA-PIP	Dihydroartemisinin–piperaquine
DSMB	Data safety monitoring board
ECG	Electrocardiogram
ELISA	Enzyme linked immunosorbent assay
EPI	Expanded programme of immunisations
EPT	Endpoint titre
GCP	Good clinical practice
GMS	Greater Mekong Subregion
Hb	Haemoglobin
HBsAg	Hepatitis B surface antigen
HBV	Hepatitis B virus
HCV	Hepatitis C virus
Hep B	Hepatitis B
HIV	Human immunodeficiency virus
IB	Investigator’s brochure
ICF	Informed consent form
ICH	International Committee on Harmonization
ICMJE	International Committee of Medical Journal Editors
IEC	Independent ethics committee
IgG	Immunoglobulin G
IM	Intramuscular
IRB	Institutional review board
IU	International unit
kg	Kilogram
MedDRA	Medical Dictionary for Regulatory Activities

**Research Proposal Submission Form
for a study involving human subject enrollment WITH
specimen collection**

Document No.: FTM ECF-033-01

Page 50 of 52

mg	Milligram
mL	Milliliter
ms	Millisecond
NANP	Asn-Ala-Asn-Pro
P. falciparum	Plasmodium falciparum
PFS	Pre-filled syringe
PI	Principal Investigator
PLT	Platelets
piMD	Potential immune-mediated disease
PQ	Primaquine
RTS,S	Particulate antigen, containing both RTS and HBs proteins
SAE	Serious adverse event
SLD-PQ	Single low dose Primaquine
SOP	Standard operating procedure
TME	Targeted malaria elimination
ULN	Upper limit of normal
WBC	White blood cells
WHO	World Health Organization

**Research Proposal Submission Form
for a study involving human subject enrollment WITH
specimen collection**

Document No.: FTM ECF-033-01

Page 51 of 52

APPENDIX D: HISTORY OF AMENDMENTS

Amendment No.	Protocol Version No.	Date issued	Author(s) of changes	Details of Changes made
1	4.0	24 August	[name]	
- Add new Co-investigator- Revise the severity grading of adverse event according to the recent PvDBPII/Matrix-M study
2	5.0	9 November	[name]	
- Change the Site Principal Investigator- Revise weight range for DHA-PIP dosing schedule (table 3) and Primaquine dosing schedule (table 4)- Add clarification of drug administration in case of vomiting- Include window period (+/- 1 day) for day 7 after vaccination (table 7)- Remove HLA typing

**Research Proposal Submission Form
for a study involving human subject enrollment WITH
specimen collection**

Document No.: FTM ECF-033-01

Page 52 of 52

APPENDIX E: SUBMISSION PACKAGE INCLUDES

No.	Submitted Documents	No. of copy
1	Cover letter from Principal Investigator's Department or Unit	1
2	Receipt of Submission Fee	1
3	Research Proposal Submission Form for a study involving human subject enrollment WITH specimen collection (FTM ECF-033-01)	1
4	Full research protocol or main protocol	1
5	Informed Consent Form, and Participant Information Sheet	1
6	Appointment Card	1
7	Subject Diary Card	1
8	Flyer	1
9	Screening Form	1
10	Case Record Form	1
11	Material Transfer Agreement (if applicable)	1
12	Investigator's Brochure	1

1 INTRODUCTION

This study is a randomized, open-label, single centre, Phase 2 trial of R21/Matrix-M™. A total of 120 healthy non-pregnant Thai adults, aged 18-55 years, inclusive, will be enrolled and randomised to one of three study groups:

- Arm 1: R21/Matrix-M™ in subjects who concurrently receive co-formulated dihydroartemisinin/piperaquine + single low dose of primaquine (SLDPQ).
- Arm 2: R21/Matrix-M™ alone.
- Arm 3: Co-formulated dihydroartemisinin/piperaquine + SLDpq

We propose to conduct a safety and immunogenicity trial of R21/Matrix-M™. The major aims of this study are to: (1) assess the safety and immunogenicity of R21/Matrix-M™ in healthy Thai adults, (2) confirm that the co-administration of antimalarial drugs with R21/Matrix-M™ does not reduce the immunogenicity of the vaccine, and (3) assess the pharmacokinetics of antimalarial drug: piperaquine in subjects who concurrently receive R21/Matrix-M™. This study will contribute to our understanding of the immunogenicity of a vaccine, which could potentially be used to help stop the spread of malaria and anti-malarial resistance in the region.

2 BACKGROUND INFORMATION

2.1 OBJECTIVES

2.1.1 PRIMARY OBJECTIVES

- To assess the safety of the R21/Matrix-M™ vaccine, with and without concurrent anti-malarial administration, in Thai adults.

2.1.2 SECONDARY OBJECTIVES

- To compare the immunologic response to R21/Matrix-M™ vaccine when concurrently given with DHA-PIP + SLD-PQ (Arm 1) with R21/Matrix-M™ vaccine alone (Arm 2) in Thai adults.
- To compare the piperaquine levels of participants who received the antimalarial drugs alone (Arm 3) with participants who received the antimalarial drugs combined vaccine (Arm 1).

2.1.3 STUDY DESIGN

This study is a randomized, open-label, single centre, Phase 2 trial of R21/Matrix-M™. A total of 120 healthy non-pregnant Thai adults, aged 18-55 years, inclusive, will be enrolled and randomised to one of three study groups:

- Arm 1: R21/Matrix-M™ in subjects who concurrently receive co-formulated dihydroartemisinin/piperaquine + single low dose of primaquine (SLDPQ).
- Arm 2: R21/Matrix-M™ alone.
- Arm 3: Co-formulated dihydroartemisinin/piperaquine + SLDpq

2.1.4 PATIENT POPULATION

Healthy Thai adults aged 18-55 years.

The inclusion and exclusion are detailed in the protocol section B5.

2.1.5 SAMPLE SIZE

The sample size calculations are based on the objective of comparing the serologic response to R21/Matrix-M™ vaccine concurrently given with DHA-PIP + SLD-PQ with R21/Matrix-M™ vaccine alone in adults instead of basing it on safety outcome. This is a Phase II trial. Sample sizes for Phase II trials are usually small, as safety is still of paramount importance. Because of this limitation, these phase II studies are usually powered on the immunogenicity/efficacy endpoints because safety events are rare and a sample size based on safety would lead to a very high sample size that would not be acceptable from ethical standpoint. Another reason why powering it on immunogenicity/efficacy (a co-primary objective) is important, is that if the vaccine has a poor immunogenicity profile then the safety question becomes redundant unless the study is a non-inferiority trial. We are optimistic that this sample size will be able to reveal important safety signals between arms which can be further explored in a phase III trial. The efficacy endpoint (Immunogenicity objective) is a co-primary objective to the safety objective. We include both “safety” and “immunogenicity” terms in the study title because both of them are key endpoints. Valid sample sizes for comparing sample sizes between two groups are usually obtained using exact test methods such as the Fisher’s exact test power calculations. This is done using simulations as sample size formulas are not well developed. To estimate the sample size we use a four-fold increase in anti-CS antibody titre as an assumed correlate of protection. For the sample size calculation, we assume that the background rate of response in the reference groups will be 5% and the true rate of anti-CS antibody response in the vaccine groups is 80%. We wish to exclude, for the vaccine, a one-tailed lower 95% CI for the reference-vaccine group difference of lower than 30%. The study aims to detect this difference with at least 90% power (because the detectable difference is big) and testing at 5% significance level. Based on these assumptions and using the method of Blackwelder for precision-based sample size calculations, a total of 20 participants per arm would be needed for arm 3 to test against each of arms 1 and 2 separately because the anticipated difference is too big. However, for arms 1 and 2 (Table 1 below), we will need more participants per group because a smaller detectable effect is anticipated. Using the Fisher’s exact test power simulations, a difference in serologic response of 30% (say 50% vs 80%) gives more than 80% power (i.e. 85% power) with a sample size of 50 participants in each of arms 1 and 2 testing at 5% significance level. Therefore, the total sample size for all the 3 arms will be 120 participants. The size of study groups is relatively small hence it is imperative to minimise potential losses. Whenever possible an attempt will be made to replace study participants should a participant be withdrawn or choose to withdraw. The stata command for obtaining the Fishers exact test power simulations is: power two proportions 0.50 0.80, test(fisher) n1(50) n2(50). This has been performed in Stata 16. The required sample sizes are summarized as follows:

Table 1. Sample size and vaccine vials required for each arm

Group	# Participants	Vaccine	Dose M0	Dose M1	Dose M2	Vaccine vials required
1	50	R21/Matrix-M™	Single standard dose (0.75mL)	Single standard dose (0.75mL)	Single standard dose (0.75mL)	300
2	50	R21/Matrix-M™	Single standard dose (0.75mL)	Single standard dose (0.75mL)	Single standard dose (0.75mL)	300
3	20	No vaccine	No vaccine	No vaccine	No vaccine	0
Total						600

Remark: R21/Matrix-M™ = adult formulation containing 10 µg of R21 and 50 µg Matrix-M in the standard dose of 0.75mL.

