5. STATISTICAL ANALYSES OF PRIMARY SAFETY ENDPOINTS

Safety analysis will be performed on patients allocated to receive vaccination. The percentage of subjects with at least one local AEs with at least one general AE (solicited and unsolicited) and with any AE during the 7-day or total follow-up period up to 28 days after the last vaccine dose and overall will be tabulated with exact 95% CI. The percentage of doses followed by at least one local AE (solicited and unsolicited), by at least one general AE (solicited and unsolicited) and by any AE during the 7-day or the total follow up period up to 28 days after the last vaccine will be tabulated with exact 95% CI. The same computations will be done for Grade 3 AEs, for any AEs considered related to vaccination and for any Grade 3 AEs considered related to vaccination. The percentage of subjects reporting each individual solicited local AE (any grade and Grade 3) and solicited general AE (any grade, Grade 3, any related, Grade 3 related, resulting in medically attended visit) during the 7-day follow-up period (Day 0-6) after each vaccine dose and overall will be tabulated for each group. Similarly, the percentage of doses followed by each individual solicited local and general AE will be tabulated, overall vaccination course, with exact 95% CI. For fever, the number and percentage of subjects reporting fever by half degree (°C) cumulative increments during the first seven days (Day 0-6) after each vaccine dose and overall will be tabulated. Similar tabulations will be performed for any fever with a causal relationship to vaccination and Grade 3 ($> 39.5^{\circ}\text{C}$) causally related fever. The percentage of subjects reporting unsolicited AEs from the date of the first vaccine dose up to 28 days after the last vaccine dose will be tabulated by group and by MedDRA preferred term with exact 95% CI. Similar tabulation will be done for Grade 3 unsolicited AEs, for any causally related unsolicited AEs and for Grade 3 causally related unsolicited AEs. The percentage of subjects reporting SAEs and pregnancies will be described in detail. The percentage of vaccinated subjects reporting AEs of specific interest (meningitis and pIMDs) will be described in detail.

Thus, in summary, the safety analysis will be as follows:

- Frequency (%) of occurrence of solicited local and general AEs within seven days (day of vaccination and six subsequent days) after each vaccination with exact 95% CI by group and severity.

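### The safety analysis gives only per-arm percentages, so the primary objective (safety with and without antimalarials) has no planned between-arm estimate

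*SAP*

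**What the plan says.** The sole listed primary objective, in SAP 2.1.1 and protocol B2.1, is "To assess the safety of the R21/Matrix-M™ vaccine, with and without concurrent anti-malarial administration, in Thai adults". The with-and-without wording corresponds to Arm 1 (vaccine plus antimalarials) and Arm 2 (vaccine alone), which are randomised 50 and 50.

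On what the sample can show about safety, the authors of SAP 2.1.5 say they are optimistic that "this sample size will be able to reveal important safety signals between arms". Protocol B5.3 has the same statement. Both sections also say that the size rests on serologic response "instead of basing it on safety outcome", and neither gives a detectable safety difference.

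For analysis, SAP 5 and protocol Appendix B 1.6.1 tabulate percentages of subjects and of doses by group, mostly with exact 95% intervals. Unsolicited events, for example, "will be tabulated by group and by MedDRA preferred term with exact 95% CI". SAP Table 4 has one column per arm, with n (%) and a 95% CI, and no contrast column. SAP heading 4.1.5, on analyses for the primary and secondary objectives, has no text under it.

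Immunogenicity is handled differently. It is listed as a secondary objective, but protocol B6.7.6 gives it between-group Fisher tests and geometric mean ratios with 95% CIs.

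**The concern.** The objective and the sizing text both look toward a contrast between arms, but no contrast is planned. The most useful safety result for later co-administration is how large an excess risk in Arm 1 over Arm 2 the data allow. Table 4 as laid out does not present it. A reader left with two separate intervals is likely to compare them by eye, and that comparison is much less sensitive than an interval for the difference. If the contrast is added only after the data are seen, its endpoints, method and direction are chosen late, in an open-label trial.

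**Working it through.** **Inputs from the documents.** Arms 1 and 2 have 50 participants each, with Fisher's exact test at the 5% level and 85% power for 50% against 80% serologic response (SAP 2.1.5). The test is taken as two-sided, because the Stata command shown has no one-sided option. The documents give no adverse event rates for this population, so every event rate below is an assumption.

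**The plan's own figure.** Power is the sum, over all outcomes (a, b) with two-sided Fisher p ≤ 0.05, of Bin(a; 50, p1) × Bin(b; 50, p2). With p1 = 0.50 and p2 = 0.80 this gives 85.3%, which reproduces the stated 85%. That figure concerns serology, not safety.

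**Per-arm intervals against a contrast.** Assume 15/50 in Arm 1 and 5/50 in Arm 2.
- Exact (Clopper-Pearson) 95% intervals: 17.9–44.6% and 3.3–21.8%. They overlap between 17.9% and 21.8%.
- Risk difference: d = 0.30 − 0.10 = 0.20.
- Wilson limits for Newcombe's method: 0.191 to 0.438 for 15/50, and 0.043 to 0.214 for 5/50.
- Lower limit: d − √[(p1 − l1)² + (u2 − p2)²] = 0.20 − √[(0.300 − 0.191)² + (0.214 − 0.100)²] = 0.043.
- Upper limit: d + √[(u1 − p1)² + (p2 − l2)²] = 0.20 + √[(0.438 − 0.300)² + (0.100 − 0.043)²] = 0.349.
- Result: +20 points, 95% CI 4.3 to 34.9; Fisher p = 0.023.

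**How much is lost by eye.** By the same enumeration with 50 per arm, the chance that the two exact intervals separate can be set beside Fisher power:

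| Assumed true rates | Fisher power | Intervals do not overlap |
|---|---|---|
| 10% v 30% | 64.0% | 31.6% |
| 20% v 40% | 51.5% | 21.1% |
| 5% v 20% | 50.8% | 21.3% |
| 10% v 35% | 82.0% | 52.9% |

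With no true difference, at assumed rates of 10% and 30%, the intervals separate in about 0.2% to 0.3% of trials.

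**Detectable difference.** The smallest higher rate, in steps of 0.5 points, that reaches 80% Fisher power with 50 per arm:

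| Assumed reference rate | Detectable rate | Difference (points) |
|---|---|---|
| 1% | 18.5% | 17.5 |
| 5% | 26.5% | 21.5 |
| 10% | 34.5% | 24.5 |
| 20% | 48.0% | 28.0 |
| 30% | 59.0% | 29.0 |
| 50% | 78.5% | 28.5 |

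A doubling from 10% to 20% has 19.5% power.

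**Rare events.** For 0/50 the exact upper 95% limit is 1 − 0.025^(1/50) = 7.1%. For 1/50 against 0/50 the Newcombe interval is −5.3 to +10.5 points around +2, so a contrast for serious events will be wide.

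**The case against.** The best defence is that descriptive safety reporting by arm is a legitimate and common choice in a phase 2 trial not sized on safety. The primary objective says assess, while both secondary objectives say compare. The primary endpoint in protocol B6.3.1 is safety in each group, and per-arm percentages match that. The sizing sentence is openly hedged and defers signals to a phase III trial, and the same paragraph says that safety events are rare and that sizing on safety would need a very large sample.

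Much of this stands. No powered safety test is required, and the limitation is largely disclosed. It does not remove the case for an estimate. A risk difference with an interval is itself descriptive, the two arms are randomised, and the documents raise signals between arms themselves.

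Two stronger readings are tempting and fail:
- A reader might infer that the plan judges arms by whether intervals overlap. Neither document states such a rule; the overlap example shows only what Table 4 leaves to the eye.
- A reader might infer that the contrast cannot be recovered. For the binary rows it can be computed from the planned counts. What is missing is a pre-specified presentation.

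A further caution concerns the contrast itself. Arm 1 has 15 visits and Arm 2 has 9; the six extra are Days 1 and 2 of three rounds, each with an adverse event assessment (protocol Tables 5 and 6). In an open-label trial, an excess of unsolicited events in Arm 1 could partly reflect more frequent questioning.

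**Conclusion.** The point holds as a gap in pre-specified estimation. Both documents frame safety with and without antimalarials and mention signals between arms, and neither plans a between-arm safety estimate. The objective is not left wholly unaddressed, because the per-arm results do describe safety in each group.

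On size, 50 per arm gives 80% power for differences of about 17 to 29 points, assuming reference rates of 1% to 50%, two-sided Fisher at 5% and no losses. It would be wrong to conclude that 80% power is reached only near 10% against 35%: that holds for a 10% reference rate alone, and the documents do not supply that rate. The change should be made because it uses data already collected; the planned tabulations remain valid without it.

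**What to change.** - Reconcile the primary safety endpoints first. Protocol B6.3.1 lists solicited events, unsolicited events and serious events; among safety outcomes, SAP 3.2 lists only serious events, over two periods.
- Add to SAP Table 4 a descriptive Arm 1 minus Arm 2 risk difference with a Newcombe 95% CI for any solicited AE, any unsolicited AE and any SAE. Add any Grade 3 solicited AE as a further row, labelled as additional because it is in neither primary list.
- Footnote the unsolicited row: the trial is open label, and Arm 1 is questioned at extra Day 1 and Day 2 visits (15 v 9 visits).
- Replace the sentence on revealing safety signals with wording such as: The trial is not powered on safety. With 50 per arm and a two-sided Fisher test at 5%, 80% power needs a difference of about 17 to 29 points for assumed reference rates of 1% to 50% (about 25 points from an assumed 10%).

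The cost is one table column, a footnote and a rewritten sentence, with no new data. The stated safety capability becomes less favourable, and the interval for SAEs will be wide.
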